6.4 Myelosuppression

Patients with leukemias and MDS usually present with abnormal peripheral blood counts at the time therapy is started and myelosuppression is an expected event during the course of therapy for acute leukemias and myelodysplastic syndromes. Thus, no dose adjustments or treatment interruptions for myelosuppression will be planned for the first 4 weeks of therapy. After this time, treatment interruptions and dose adjustments may be considered on an individual basis. The following guidelines can be used to consider treatment:

- 6.4.1** Patients with neutropenia or thrombocytopenia as a consequence of the disease do not require treatment interruptions for myelosuppression. Dose-reductions in these patients should be considered in an individual case and discussed with the PI. The following guidelines can be used for these patients:
 - 6.4.1.1** Patients with a response and pre-cycle counts of neutrophils $>1 \times 10^9/L$ and platelets $>50 \times 10^9/L$ who have sustained low counts of neutrophils $<0.5 \times 10^9/L$ or a platelet count $<20 \times 10^9/L$ for more than 2 consecutive weeks in the current cycle, may receive a subsequent course at 1 dose level reduction. A reduction of 2 dose levels may be considered if the myelosuppression was deemed severe and life threatening by the treating physician, and if it is in the patient's best interest.
 - 6.4.1.2** If there are persistent peripheral blood blasts, or the bone marrow shows $>5\%$ blasts, may continue treatment regardless of neutrophil and platelet count and give supportive care as needed.
 - 6.4.1.3** If no marrow evidence of leukemia, may hold therapy until recovery of granulocytes to $\geq 1 \times 10^9/L$ and platelets $\geq 60 \times 10^9/L$,

then resume at same or 1 lower dose level according to guidelines mentioned above.

6.5 Inpatient Dose Escalation for Patients Treated at Dose Level -1 or Lower

Inpatient dose escalation will be permitted for these patients provided:

- 6.5.1** Patient has completed ≥ 1 cycle at dose level -1 or lower, and
- 6.5.2** Patient has not experienced any grade 3 or higher non-hematologic toxicity, and
- 6.5.3** Patient has not experienced hematologic DLT, and
- 6.5.4** At least 3 patients have been treated at the next higher dose level and followed for at least 28 days without experiencing DLT.
- 6.5.5** Patients who have experienced no QTc prolongation above 480 msec in whom optimal anti-leukemia effect has not been reached may have the dose of quizartinib increased to by one dose level. Patients who have such dose escalation will have an EKG done 24 hours and 7 days after dose escalation. No dose escalation above 90 mg/day will be allowed.
- 6.5.6** Because of the increased risk of QTc prolongation in women treated at doses > 90 mg/day in prior studies with AC220, dose escalation above 90 mg/day is not allowed in women.

7.0 AGENT FORMULATION AND PROCUREMENT

7.1 Quizartinib (AC220)

7.1.1 Description

The chemical name of the investigational product, quizartinib, is N-(5-tert-Butyl-isoxazol-3-yl)-N'-[4-[7-(2-morpholin-4-yl-ethoxy)imidazo[2,1-b][1,3]benzothiazol-2-yl]phenyl] urea dihydrochloride salt.

AC220 is supplied as tablets each containing 30 mg AC220 (26.5 mg free base) and 300 mg HP β CD. The tablets also contain microcrystalline cellulose, magnesium stearate, and Opadry® II 85F18422 white film coating. They are packaged in high density polyethylene bottles, each containing 30 tablets, with child-resistant caps.

7.1.2 Clinical Pharmacology

Analysis of human plasma samples demonstrate that AC220 is orally bioavailable with a long effective half-life, estimated to be about 1.5 days. In addition, AC220 exhibits minimal peak and trough variation of plasma levels with once daily dosing. In addition, a pharmacologically active metabolite, AC886, has been identified in plasma and urine samples, which has a slightly longer half-life of about 2 days. Since food has been shown to affect absorption in animals, AC220 should be taken in the morning on an empty stomach.

7.1.3 Potential Indications and Usage

AC220 is currently being evaluated as a treatment for patients with AML who are not candidates for standard therapy (Phase 1 study), or whose disease is refractory to, or has relapsed, following standard therapy in a multiple cohorts of patients (Phase 2 study) irrespective of age. Patients with and without FLT3 mutations are being investigated. It is planned to assess the safety and efficacy of AC220 as monotherapy and/or in combination with other agents for the treatment of AML and also in other oncology and disease indications.

7.1.4 Dosing

Each patient will receive or be instructed to take AC220 oral tablets at the assigned dose once a day on an empty stomach at least 1 hour before or 2 hours after a meal in the morning for 28 consecutive days as 1 cycle of treatment.

7.1.5 Selection and Timing of Dose

Each treatment cycle consists of 28 consecutive days. AC220 will be taken orally once a day on an empty stomach (i.e., 1 hour before or 2 hours after a meal) in the morning. The starting dose in the Phase 2 monotherapy study was 200 mg/day. Due to a higher than anticipated rate of QT prolongation, lower doses of 90mg/day in females and 135mg/day in males was pursued after the initial 17 subjects were enrolled out of a total of 333 subjects in the Phase 2 study.

7.1.6 Packaging and Labeling

Please refer to the Pharmacy Manual for packaging and labeling information.

7.1.7 Study Drug Preparation

Please refer to the Pharmacy Manual for packaging and labeling information.

- 7.2 **AZA and cytarabine:** these drugs are commercially available and will be handled as per the packet insert and standards in the MDACC investigational pharmacy.
- 7.3 **Disposition of unused drug:** all unused drug will be disposed of per institutional guidelines and procedures.

8.0 CORRELATIVE/SPECIAL STUDIES (Optional)

In patients treated with FLT3 inhibitors, the degree of FLT3 inhibition in vivo has been shown to be an important parameter in determining clinical response (Levis et al 2011 Blood 117:3294). In addition, the plasma levels of FLT3 ligand (FL) may influence the degree of in vivo inhibition (Sato et al 2011 Blood 117:3286). In patients treated with quizartinib and 5-azacitidine or low-dose AraC (LDAC), it is hypothesized that in vivo FLT3 inhibition, which may be impacted by FL levels, will influence clinical responses. Therefore, we propose to measure in vivo FLT3 inhibition and FL levels in patients enrolled on this trial. We will collect whole blood into a 10 cc heparinized (green top) vacutainer tube pre-treatment and on Days 1, 8, and 15 of each cycle up to the first 4 cycles (all ± 2 days); (therefore 12 samples maximum per patient). For each time point, therefore, approximately 8 cc whole blood will be collected. The blood will be centrifuged to separate the cellular fraction, and the plasma (3-5 cc per sample) will be transferred into a separate tube for frozen storage. Samples will be shipped in batches every month to the laboratory of [name]:

[name] MD PhD
[name]
[name]
[name]

For analysis, frozen plasma will be thawed rapidly, then stored on ice. For FL levels, 200 microliters will be used in an ELISA-based assay system (R&D). For determination of in vivo FLT3 inhibition, the remaining plasma will be assayed using a Plasma Inhibitory Activity assay for FLT3 by incubating 1 cc plasma with the FLT3/ITD-expressing Molm14 cell line, then performing immunoblotting for phospho-FLT3 as described (Levis et al 2006 Blood 108:3477). The degree of in vivo FLT3 inhibition will be calculated as a percent of the baseline (from the baseline sample collected pre-treatment). Results will be entered into a spreadsheet and returned to the study PI when all samples have been analyzed.

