1.0 OBJECTIVES

1.1 Primary Objectives

1.1.1 Phase I: To determine the DLT and MTD of the combination of quizartinib (AC220) with either 5-azacitidine (AZA) or low-dose cytarabine (LDAC) in patients with acute myeloid leukemia (AML) or high-risk myelodysplastic syndrome (MDS).

1.1.2 Phase II: To determine the clinical activity of the combination of quizartinib with either AZA or LDAC in patients with AML or MDS.

1.2 Secondary Objectives:

1.2.1 Phase I: To determine the clinical activity of the combination of quizartinib with either AZA or LDAC in patients with AML or MDS.

1.2.2 Phase II: To determine the safety of the combination of quizartinib with either AZA or LDAC in patients with AML or MDS.

1.2.3 Both:

1.2.3.1 To determine the induction of hypomethylation, DNA damage and FLT3 signaling during therapy with this combination and its correlation with response.

1.2.3.2 To determine the effect of this combination therapy on plasma levels of FLT3-ligand

1.2.3.3 To determine the pharmacodynamics of this combination therapy in patients with AML or high-risk MDS.

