4.1.4 For Phase I and II

4.1.4.1 ECOG Performance Status ≤ 2

4.1.4.2 Adequate liver (bilirubin $\leq 2x$ ULN, ALT $\leq 2.5x$ ULN) and renal (creatinine $\leq 2x$ ULN) function. For patients with suspected liver infiltration from leukemia, ALT should be $\leq 5x$ ULN.

4.1.4.3 Serum potassium, magnesium, and calcium (normalized for albumin) levels should be at least within institutional normal limits.

4.1.4.4 Patients must provide written informed consent.

4.1.4.5 Patients must have been off chemotherapy for 2 weeks prior to entering this study, unless there is evidence of rapidly progressive disease, and must have recovered from the toxic effects of that therapy to at least grade 1. Use of hydroxyurea for patients with rapidly proliferative disease is allowed before the start of study therapy and for the first four weeks on therapy. The additional days of Hydrea after 28 is permitted as clinically indicated, on case by case basis and after discussion with the PI. Other agents given transiently with the intention to control rapid proliferation such as 1-2 doses of single agent ara-C or few doses of sorafenib are also allowed.

4.1.4.6 Women of childbearing potential must practice contraception. Women considered not of childbearing potential include any of the following: no menses for at least 2 years or menses within 2 years but amenorrheic for at least 2 months and luteinizing hormone (LH) and follicular stimulating hormone (FSH) values within normal range (according to definition of postmenopausal for laboratory used) or bilateral oophorectomy or radiation castration and amenorrheic for at least 3 months. Females of childbearing potential should practice effective methods of contraception. Effective methods of contraception include barrier methods (e.g., condoms, diaphragm), spermicidal jelly or foam, oral, depo provera, or injectable contraceptives, intrauterine devices, tubal ligation, and abstinence. Male patients with female partners who are of childbearing potential should also practice contraception.

4.1.5 Negative urine or serum pregnancy test.

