5.2 Schedule

5.2.1 Patients will be treated according to the following schedule:

- AZA will be administered subcutaneously (SQ) or intravenously (IV) for 7 days of every cycle (Days 1-7) as determined by the treating physician. Both SQ and IV forms of administration are FDA approved and considered interchangeable. Patients may start receiving AZA IV and changed to SQ at any time (and vice versa) as needed based on patient and physician preference. AZA is administered in the clinic or chemotherapy administration area.
- Cytarabine will be administered SQ twice daily for 10 days of every cycle (Days 1-10) as determined by the treating physician. Cytarabine can be self-administered by the patient.
- Quizartinib will be administered orally daily for 28 days of every cycle. For the first cycle only, quizartinib will be administered starting on day 5 of the cycle. All subsequent cycles quizartinib will start concomitantly with AZA or cytarabine.

5.2.1.1 The starting and target dose is dose level 1.

Table 1(a): Dose reduction and escalation for Cytarabine + AC220 treatment arm

Dose Level	Cytarabine (mg BID x 10 days)	AC220 (mg/d, uninterrupted)
-3	10	30
-2	15	30
-1	20	30
1 (Starting and target dose)	20	60
2	20	90

Table 1(b): Dose reduction and escalation for AZA+ AC220 treatment arm

Dose Level	AZA (mg/m ² /d x 7 days)	AC220 (mg/d, uninterrupted)
-3	25	30
-2	50	30
-1	75	30
1 (Starting and target dose)	75	60
2	75	90

- 5.2.1.2** Dose reductions beyond those mentioned in this table or different to the doses specified should be discussed with the PI and documentation of the justification recorded in the chart.
- 5.2.2** Patients will be assigned to treatment arm by physician's choice and according to the availability of slots.
- 5.2.2.1** Treatment arm is defined by the use of each of the possible chemotherapy agents (i.e., AZA + AC220 is one treatment arm and Cytarabine + AC220 is another treatment arm).
- 5.2.2.2** Patients in Cohort 2B (FLT3 WT) will only be treated with AZA + AC220. The combination with cytarabine will not be explored in this subset of patients in this study.
- 5.2.3** The first 6 patients on each cohort will receive dose level 1. At least 3 of the patients will be females.
- 5.2.3.1** A cohort is defined by each dose level.
- 5.2.4** Prior to advancing/changing cohorts a cohort summary will be completed and submitted to the Medical Monitor in the IND Office.

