9.0 PATIENT EVALUATION (See Appendix AA)

9.1 Pre-Treatment Evaluation

All pretreatment studies should be obtained within 14 days of entry into the trial, unless otherwise stated.

- 9.1.1 A complete history and physical, documentation of all measurable disease, concomitant medications and performance status.
- 9.1.2 CBC, platelet count, differential (differential can be omitted if WBC is $\leq 0.5 \times 10^9/L$).
- 9.1.3 Creatinine, total bilirubin, ALT, potassium, magnesium, calcium, sodium, chloride, CO₂, uric acid, phosphorus, and BUN.
- 9.1.4 Pregnancy test (urine or plasma) in females of childbearing potential, should be performed 48 hours before initiation of study.
- 9.1.5 Bone marrow aspirate during the last 21 days preceding study initiation. Cytogenetics will be obtained prior to therapy (results from prior analysis can be used for this purpose).
- 9.1.6 Evaluation of FLT3 if not done within 90 days, provided there has been no intervening therapy other than hydroxyurea or isolated single-agent doses of cytarabine.
- 9.1.7 EKG and ECHO and/or MUGA will be performed before initiating study treatment if not done within 28 days.
- 9.1.8 Pretreatment optional correlative studies (see Section 8.0)

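### FLT3 inhibition is scaled to a pre-treatment plasma sample that may follow sorafenib, and exposed baselines are not flagged, so inhibition can be understated in those patients by an unknown amount

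*Combined protocol and SAP*

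**What the plan says.** - **The measure.** Section 8.0 reads phospho-FLT3 after "incubating 1 cc plasma with the FLT3/ITD-expressing Molm14 cell line". The result is then scaled to the patient's own starting sample: "The degree of in vivo FLT3 inhibition will be calculated as a percent of the baseline (from the baseline sample collected pre-treatment".
- **Its use.** Objective 1.2.3.1 covers "FLT3 signaling during therapy with this combination and its correlation with response". Section 8.0 gives the working hypothesis that the degree of inhibition affects clinical response.
- **Treatment before the baseline.** For both phases, section 4.1.4.5 says of agents given briefly against rapid proliferation: "such as 1-2 doses of single agent ara-C or few doses of sorafenib are also allowed". It gives no maximum number of sorafenib doses and no interval before the baseline draw.
- **Timing of the draw.** Section 9.1: "All pretreatment studies should be obtained within 14 days of entry into the trial, unless otherwise stated". Nothing ties the tube to the last sorafenib dose.
- **Quizartinib start.** Section 5.2.1: "For the first cycle only, quizartinib will be administered starting on day 5 of the cycle". A cycle 1 day 1 tube therefore also precedes quizartinib.
- **Safeguards.** For the FLT3 mutation test, section 9.1.6 accepts an earlier result only if nothing beyond hydroxyurea or isolated cytarabine doses came in between. The plasma baseline has no matching condition. Section 8.0 names no inhibitor-free reference plasma, exposure flag or sensitivity analysis.

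**The concern.** The assay responds to whatever FLT3-inhibiting drug is in the plasma and does not tell quizartinib from any other inhibitor. If the pre-treatment plasma already contains one, the denominator of the ratio is too low and quizartinib appears to add less than it does. The error goes one way and is confined to patients whose baseline followed sorafenib.

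Those patients are given sorafenib because their disease is proliferating fast, so they may also differ in response. The planned analysis links inhibition to response. A mixture of clean and exposed baselines can weaken that link, or create one if exposure is itself related to response. At stake is the reading of an optional secondary objective, not the trial's main conclusions.

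**Working it through.** The plan gives no figure to reproduce, so the check is algebra followed by an illustration under stated assumptions.

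**1. The formula.** Let q be the true on-treatment inhibition and s the inhibition already present in the baseline plasma, both against inhibitor-free plasma. The on-treatment signal is 1 - q and the baseline signal is 1 - s. The plan's ratio gives

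reported inhibition = 1 - (1 - q)/(1 - s).

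The shortfall against q is (1 - q) × s/(1 - s), which is positive whenever s > 0 and q < 1.

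**2. Numbers for one patient with true inhibition of 90%.**

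| Baseline signal (1 - s) | Calculation | Reported inhibition |
|---|---|---|
| 100% | 1 - 0.10/1.00 | 90% |
| 80% | 1 - 0.10/0.80 | 87.5% |
| 50% | 1 - 0.10/0.50 | 80% |
| 20% | 1 - 0.10/0.20 | 50% |

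The loss is small when true inhibition is nearly complete (q = 0.95, s = 0.25 gives 93.3%) and large when it is partial (q = 0.70, s = 0.50 gives 40%). If s exceeds q the result is negative (q = 0.70, s = 0.75 gives -20%).

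**3. Which tube is the baseline.** Section 8.0 asks for a pre-treatment sample plus days 1, 8 and 15 of up to four cycles, with a maximum of 12. Since 3 × 4 = 12, a separate pre-treatment tube would make 13, so baseline and cycle 1 day 1 may be the same tube. Either tube precedes quizartinib, and either could follow sorafenib.

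**4. Effect on the correlation with response.** The exposed share and the residual inhibition are not in the documents, so both are varied. Simulation of 400,000 patients: remaining signal on quizartinib f ~ beta(1.5, 6); logit P(response) = 1 - 5f, about 50% responding; observed value f/baseline, capped at 1.5; exposure unrelated to response. The correlation is between remaining phospho-FLT3 and response, hence negative. Without exposed patients it is -0.30.

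| Baseline signal if exposed | 5% exposed | 10% exposed | 20% exposed |
|---|---|---|---|
| 20-50% | -0.25 | -0.23 | -0.21 |
| 50-90% | -0.297 | -0.291 | -0.285 |
| 80-100% | not tabulated | not tabulated | -0.301 |

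In the most severe row the rank (Spearman) correlation falls less, from -0.295 to about -0.255 with 20% exposed.

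A second set of assumptions (q ~ beta(8, 2), true correlation of inhibition with response 0.41, 10-30% exposed) gives 0.39 to 0.37 for s of 0.10-0.50 and 0.33 to 0.30 for s of 0.25-0.75. That is 4% to 28% attenuation.

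**5. If exposed patients also respond differently** (baselines at 20-50%, 10% and 20% exposed):
- Inhibition has no effect and exposed patients respond less often (logit -1): the planned measure shows -0.08 and -0.11 where the truth is 0.
- Inhibition has its effect and exposed patients respond more often (logit +1): a true -0.31 and -0.30 reads as -0.15 and -0.10.

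**6. After the fix.** With exposed baselines left out, s = 0, the formula returns q, and the simulated correlation of step 4 is again -0.30.

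**The case against.** The strongest case against the point has five parts.

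- **The premise is external.** No section says that sorafenib inhibits FLT3. This stands as a declared assumption. The algebra applies to any FLT3 inhibitor in the baseline plasma.
- **The reach is unknown.** A tube drawn before sorafenib, or after it has cleared, is clean. For newly diagnosed phase II patients, section 4.1.3 names only hydroxyurea and single-agent ara-C as acceptable prior therapy, while 4.1.4.5 covers both phases. Exposure in that group is therefore unclear until the two are reconciled. This stands: the size of the effect cannot be settled from the documents.
- **The large figures need severe inputs.** The fall to -0.21 needs baselines at 20-50% of the inhibitor-free level and a Pearson correlation on a ratio. The sampling standard deviation of this correlation is about 0.13 at n = 50, so a shift of 0.05 to 0.09 is below one standard deviation. This stands, and it is why a range is given.
- **The problem is partly visible.** Negative inhibition would give some cases away, and section 9.1.1 already records concomitant medications. That is true, but a moderately low baseline leaves no such trace, and the plan does not say that the medication record will be used this way.
- **Little depends on it.** Section 8.0 is optional, and section 12.4 specifies no test or model for this measure. This stands.

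A reader might infer three stronger things that the documents do not support. The first is that the planned correlation is certainly biased by a material amount; the inputs needed to say so are missing. The second is that waiving the two-week washout ("Patients must have been off chemotherapy for 2 weeks prior to entering this study, unless there is evidence of rapidly progressive disease") adds to the problem; that sentence concerns chemotherapy, and nothing in the documents links it to a lower baseline phospho-FLT3. The third is that own-baseline scaling should be dropped for everyone. It is a defensible within-patient choice when the baseline is clean, and whether the cited assay method already includes a control lane cannot be seen from here.

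**Conclusion.** The point holds in a limited form. Followed as written, section 8.0 understates quizartinib's FLT3 inhibition in any patient whose baseline plasma still contains an active FLT3 inhibitor, and section 4.1.4.5 makes that possible. The direction is certain given the assumption about sorafenib. The size is not: a true 90% reads as anything from 87.5% to 50% over the baselines shown. With 5-20% of patients exposed, the correlation of -0.30 moves by almost nothing or to -0.21 at worst. A differential bias is possible but rests on the further assumption that exposed patients respond differently. Determination of the MTD is untouched, as are the primary endpoint and stopping rules. The change is worth making because it is cheap, not because the harm is shown to be large.

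**What to change.** Add to section 8.0:

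1. State which tube is the baseline. Flag every patient who received sorafenib or another FLT3 inhibitor before that draw, using the medication record of section 9.1.1 and adding the date of the last dose.
2. Run the main inhibition-response analysis in patients with an unexposed baseline, keeping percent of own baseline as the measure there. Show all patients as a sensitivity analysis, and report the number flagged.
3. If the assay already runs an inhibitor-free control lane, also report pre-treatment and on-treatment phospho-FLT3 relative to it. This lets exposed patients be displayed on a usable scale.

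The cost is one data field, a few sentences and no extra blood. The downside is slightly fewer patients in an optional secondary analysis, whose main result would then describe only patients with an unexposed baseline. No eligibility or treatment rule changes.
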